Full study protocol and statistical analysis plan

Official Title of the study:

An analysis soluble endoglin and matrix metalloproteinase 14 with Elisa method in the diagnosis and severity of early/late-onset preeclampsia

Date of the document:

June 2018.

Contents:

- 1. Participant Flow
- 2. Baseline Characteristics
- 3. Outcome Measures
- 4. Endpoints of the study
- 5. Limitations and Strengths
- 6. Certain Agreements
- 7. Results Point of Contact

1. Participant Flow

Recruitment Details

The study was conducted at Cengiz Gokcek Women's and Children's Hospital, Gaziantep, Turkey at department of obstetric and gynecology between date of January 2018 and December 2018. The study protocol was designed according to the Declaration of Helsinki, and the institutional ethical review board of Gaziantep University approved the study (Reference number: 2018/91). The study was conducted with 30 late-onset preeclampsia patients as group 1 (gestational age \geq 34 weeks), 33 patients with normal pregnancies as group 2 (gestational age \geq 34 weeks), 31 early-onset preeclampsia patients as group 3 (gestational age < 34 weeks), and 31 patients with normal pregnancies as group 4 (gestational age < 34 weeks). Finally, The authors consecutively recruited 61 pregnancies complicated with preeclampsia, and 64 healthy pregnancies will select for the control group. All participants included in the study gave oral and written informed consent.

Pre-assignment Details

The authors firstly were assessed the recruited people to ensure meeting the inclusion and

exclusion criteria.

The inclusion criteria were maken according to the official documents.

Arm/Group Information *

There are four groups in the study.

Arm/Group Title *

Preeclampsia groups = Group 1, group 3 Control groups= Group 2, group 4

2. Baseline Characteristics

In the analysis of variables, t-test was used for comparison of two groups and one-way analysis of variance was used for comparison of three groups. In addition, the demographic information of the variables were determined by frequency and percentage analyzes. The Statistical Package for the Social Sciences (IBM SPSS Statistics for Windows, Version 22.0,

IBM Corp., NY, USA).

3. Outcome Measures

Every woman in the study population underwent obstetric ultrasound examination and fetal-maternal assessment was carried out by one of the authors. Obstetric anamneses were obtained from all subjects. The demographic data for gestational age, gravidity, parity, maternal age and BMI was recorded. Maternal venous blood samples were taken for measurement of serum MMP-14 and s-ENG levels after the diagnosis of early/late onset preeclampsia in outpatient clinic. These samples quickly centrifuged at 1,500 g for 10 min, plasma and serum samples were separated and serum samples were stored at -80 C until the day of measurement. The participants with early/late onset preeclampsia were hospitalized. In early onset preeclampsia, a betamethasone injection was administered immediately after hospitalization. The pregnancy was immediately terminated in emergencies arising from maternal or fetal causes. Otherwise, blood pressure was measured every four hours during periods of rest. Hypertension can be confirmed within a shorter interval in patients with blood pressure >110mm Hg diastolic and >160mm Hg systolic in order to give timely antihypertensive treatment. Delivery should be postponed for at least 24-48 hours if maternal/fetal status permit. A betamethasone injection for lung maturation (two dosages of 12 mg at 24 h intervals) was given within the said period. The control group's samples were obtained during routine obstetrical care examination in the third trimester of pregnancy. Then these pregnant women were followed-up until delivery. The participants with late onset preeclampsia (LOPE) were also hospitalized and terminated. The control groups' samples obtained during the routine obstetrical care examination in the third trimester of pregnancy. Then these pregnant women were followed-up until the delivery. Four groups compared in terms of maternal age, BMI, gravida, parity, week of gestation, systolic/diastolic blood pressure, total protein in spot urine sample, white blood cell (WBC) count, hemoglobin, platelet count, blood urea nitrogen, creatinine, liver function tests (AST, ALT), MMP-14, s-ENG, and infant weight at delivery. The s-ENG level was measured with a commercially avaliable ELISA kits which is produced to detect human s-ENG level with a high sensitivity and specificity (Rel Assay Diagnostics, Gaziantep, Turkey). The measurements were done in accordance with company's protocol. The kit uses Sandwich-ELISA principle. Serum MMP-14 levels were determined using a commercially available ELISA kit, the Human MMP14 ELISA Kit (Rel Assay Diagnostics, Gaziantep, Turkey),

according to the manufacturer's instructions. Human MMP-14 ELISA kit is based on the principle of biotin double antibody sandwich technology.

4. *Endpoints of the study:*

The primary endpoint in this analysis is to evaluate the value of serum matrix metalloproteinase-14 levels (ng/ml) in preeclampsia patients and also address its relationship with its severity.

The secondary endpoint in this analysis is to evaluate the value of serum soluble endoglin levels (ng/ml) in preeclampsia patients and also address its relationship with its severity.

5.Limitations and strengths:

The main limitation of our study is the small number of patients. We do not have prepregnancy BMI of patients and controls. Levels of s-ENG and MMP-14 could also be measured in different compartments such as placenta, umbilical cord serum and amniotic fluid.

As for the strengths of the study, none of the patients had any treatments for preeclampsia and active labor

6. Certain Agreements

The authors declare that they have no conflict of interest.

7. Results Point of Contact

Corresponding Author: [name], Cengiz Gokcek Public Hospital, Department of Obstetrics

and Gynecology, Gaziantep/Turkey, [contact]

Adress: [name]

GAZİANTEP

GSM: [contact]

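### The one inferential sentence (t-test for two groups, ANOVA for three) does not match the four-group comparison and names no deciding contrast for MMP-14 or s-ENG

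*Combined protocol and SAP*

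**What the plan says.** The sentence on tests stands under section 2, Baseline Characteristics: "t-test was used for comparison of two groups and one-way analysis of variance was used for comparison of three groups". It is introduced as applying to the analysis of variables in general, and no other test appears in the document.

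Section 1 (Arm/Group Information) states "There are four groups in the study", and Arm/Group Title lists them as "Preeclampsia groups = Group 1, group 3 Control groups= Group 2, group 4". Recruitment Details gives the sizes: 30 late-onset cases (group 1) and 33 controls (group 2) at 34 weeks or later, then 31 early-onset cases (group 3) and "31 patients with normal pregnancies as group 4 (gestational age < 34 weeks").

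Section 3 (Outcome Measures) reads "Four groups compared in terms of maternal age, BMI, gravida, parity, week of gestation, systolic/diastolic blood pressure"; that list goes on to include MMP-14 and s-ENG. Cases were sampled after diagnosis. Control "samples were obtained during routine obstetrical care examination in the third trimester of pregnancy".

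Section 4 states "The primary endpoint in this analysis is to evaluate the value of serum matrix metalloproteinase-14 levels (ng/ml) in preeclampsia patients", together with its relationship to severity, and ranks s-ENG second in the same form. It names no comparator, contrast, significance level or adjustment. An early/late question is raised only by the title ("in the diagnosis and severity of early/late-onset preeclampsia") and by the group definitions.

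**The concern.** The four groups cross disease with gestational stratum, so different comparisons answer different questions. Groups 1 v 2 and 3 v 4 compare cases with controls inside a stratum. Group 1 v 3 compares cases at different gestational ages. A four-group F test responds to any difference, including one due to gestational age alone.

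The plan names none of these for either marker, and its ANOVA clause refers to a number of groups that no described comparison has. The deciding comparison could therefore be settled after the marker results are known, and the false-positive rate would depend on how many pairs were tried. A statement about early versus late onset could also rest on a comparison that cannot tell onset from gestational age.

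**Working it through.** **Inputs.** Group sizes 30/33/31/31 come from section 1. They are consistent: 30 + 31 = 61 cases, 33 + 31 = 64 controls, 125 in all. The documents give no significance level, SD, effect size or power, so there is no design figure to reproduce. Assumed below: two-sided 5% per test, normal data, equal SD, differences in SD units.

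**Number of contrasts.** Four groups give 4 × 3 / 2 = 6 pairs per marker.

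**False positives per marker, all four means equal.**

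| Reading of the plan | At least one false positive |
|---|---|
| Four-group F required before any pair | about 5% |
| 1 v 2 and 3 v 4, unadjusted: 1 − 0.95² | 9.75% (simulated 9.7%) |
| 1 v 2 and 3 v 4 with Holm | 4.9% |
| All six pairs, unadjusted (simulated) | about 20% |

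**Does requiring the F test first protect 1 v 2 and 3 v 4?** Only when the strata do not differ. With a shift between strata but no disease effect, the F test tends to reject because of the shift, and the two t-tests are then in effect unadjusted. At assumed shifts of 0.5 and 1 SD, at least one of the two is falsely rejected in about 9% and 10% of studies.

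**What 1 v 3 and the F test respond to (illustrative).** With an assumed stratum shift and no disease or onset effect:

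| Assumed shift (SD) | 1 v 3 rejects | Four-group F rejects |
|---|---|---|
| 0.25 | 16% | 18% |
| 0.5 | 48% | 63% |
| 0.75 | 82% | 95% |
| 1.0 | 97% | 99.8% |

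These rejections are correct as statements that the means differ. They are wrong only if read as an effect of preeclampsia or onset. Each of 1 v 2 and 3 v 4 stays at 5% if cases and controls within a stratum have the same weeks.

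**If weeks differ within a stratum (illustrative).** Assume early cases spread over 24–34 weeks, early controls over 28–34, and linear drift of 0.1 / 0.15 / 0.2 SD per week. Then 3 v 4 falsely rejects in 11.4 / 19.0 / 28.6%. With week in the model it returns to 4.5–5.1%. With equal 28–34 ranges and 0.15 SD per week it is 5.0% without the week term.

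**Precision of the alternatives (before a week term, 121 df, 80% power).**

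- 1 v 2: SE = √(1/30 + 1/33) = 0.252. 3 v 4: SE = √(1/31 + 1/31) = 0.254. Detectable difference 0.71–0.72 SD at 5%, 0.79 SD at the first Holm step (2.5%).
- Stratum-adjusted preeclampsia contrast, the mean of (1−2) and (3−4): SE = ½ √(1/30 + 1/33 + 1/31 + 1/31) = ½ × 0.358 = 0.179. Detectable difference 0.51 SD; power at 0.5 SD 79%.
- Interaction (3−4) − (1−2): SE = 0.358. 95% CI half-width 0.71 SD, detectable difference 1.01 SD, power at 0.5 SD 28%.

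**The case against.** The strongest reply is that nothing is wrong with the tests themselves. The design supplies controls for each stratum, a t-test of 1 v 2 or 3 v 4 fits it, and the word for three may be a slip for four. The first two points stand: the defect is an unnamed contrast and an ANOVA clause that matches no comparison described. The slip is possible, but correcting the word alone would still leave the deciding contrast open.

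A second reply is that 20% is a worst case. That also stands. The plan does not say that six unadjusted pairs will be tested, and under equal means an F test required first brings the rate to about 5%. The plan does not state that gate either, and it gives little protection once the strata differ.

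A third is that MMP-14 is ranked above s-ENG. The ranking orders the markers. It does not choose among the contrasts within a marker or set a rule for testing both.

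A reader might infer that the plan intends to read 1 v 3 or an omnibus F as an onset effect. The documents do not say so, and the endpoints contain no early-versus-late hypothesis. A reader might also infer from the past tense and the exact group sizes that the contrast was chosen with results in hand. The documents do not show that. They only leave it open.

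**Conclusion.** The point holds as a gap in specification that should be fixed. The stated rule does not match the four-group comparison, and no contrast or multiplicity rule is given for either marker. Depending on how the sentence is read, the per-marker false-positive rate is about 5% to 20% when all means are equal, at an assumed two-sided 5%. These rates need no assumption about gestational trend.

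The drift figures are illustrative only, because the documents give no marker SD or gestational trend. They show which comparisons are exposed, not how large any bias is in this study. The within-stratum tests are not immune either. Cases were sampled at diagnosis and controls at a routine third-trimester visit, so weeks may differ within a stratum; the documents do not show whether they do.

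**What to change.** Correct or explain the reference to three groups, and replace the sentence with one linear model per marker on all 125 women. The model has preeclampsia, gestational stratum, their interaction, and the recorded week of gestation (taken here to be the week at sampling) in the main analysis.

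- **Deciding contrast:** one stratum-adjusted preeclampsia effect for MMP-14, two-sided 5%. Report the same contrast for s-ENG as secondary.
- **Stratum-specific results:** 1 v 2 and 3 v 4 from the model, Holm-adjusted within marker.
- **Early versus late onset:** only (3−4) − (1−2), as an exploratory estimate with 95% CI. Do not read 1 v 3 or an omnibus F as an onset effect.
- **Scale:** fix raw or log for each marker in advance.
- **Timing:** state whether marker results had been seen when the contrasts were named. If they had, adjustment cannot restore prespecification.

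The cost is wording and one model per marker; week of gestation is already recorded. The pooled contrast averages over strata and can hide an effect confined to one. Holm raises the stratum-specific detectable difference from about 0.71 to 0.79 SD. The week term costs some precision if weeks differ between cases and controls. The interaction is imprecise, so a null result must not be read as no early/late difference.

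A smaller change, keeping the t-tests but naming 1 v 2 and 3 v 4 with Holm, would close the multiplicity gap within each marker. It would leave week of gestation and the onset question unaddressed. The severity half of each endpoint is outside this fix and needs its own analysis.

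### The case-control comparison of MMP-14 and s-ENG is unadjusted, and no matching or restriction on parity, maternal age or BMI is stated although all three are recorded

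*Combined protocol and SAP*

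**What the plan says.** - **Recruitment (section 1, Participant Flow).** For cases: "The authors consecutively recruited 61 pregnancies complicated with preeclampsia". For controls: "64 healthy pregnancies will select for the control group". How controls are chosen is not described.
- **Alignment.** Controls are split at 34 weeks to mirror the cases: 30 late-onset cases (group 1) with 33 controls (group 2), and 31 early-onset cases (group 3) with "31 patients with normal pregnancies as group 4 (gestational age < 34 weeks". No other matching factor is mentioned.
- **Eligibility (section 1, Pre-assignment Details).** "The inclusion criteria were maken according to the official documents". Those documents are not named and the criteria are not listed.
- **Maternal data (section 3, Outcome Measures).** "The demographic data for gestational age, gravidity, parity, maternal age and BMI was recorded". Their use is given in the same section: "Four groups compared in terms of maternal age, BMI, gravida, parity, week of gestation", in a list that also holds laboratory values and the two markers.
- **Analysis (section 2, Baseline Characteristics).** "t-test was used for comparison of two groups and one-way analysis of variance was used for comparison of three groups". No regression, ANCOVA or stratification by maternal factors appears anywhere in the document.
- **Limitations (section 5).** "We do not have prepregnancy BMI of patients and controls". Small numbers are also acknowledged; confounding is not mentioned.

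**The concern.** Both endpoints (section 4) ask what a marker's serum level is worth in preeclampsia. That rests on comparing cases with controls drawn by a different and undescribed route. If parity, age or body size differs between the two sources and also relates to the marker, part of the observed difference comes from who the women are rather than from the disease. An unadjusted t-test or ANOVA passes that part straight into the result. The group comparisons on age, BMI, gravidity and parity may reveal an imbalance, but they do not correct for it, and the plan does not say what would follow if one were found.

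At stake is the reading of the primary (MMP-14) and secondary (s-ENG) case-control differences. Each endpoint also has a severity part. That is a question within cases, and control selection does not touch it.

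**Working it through.** **No design figure to reproduce.** The documents give no significance level, SD, effect size or sample-size calculation. The group counts agree: 30 + 31 = 61 cases, 33 + 31 = 64 controls, 125 in total.

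**Step 1: can a bias of this kind enter?** Setting the sections side by side: no stated matching beyond the 34-week split (section 1), unadjusted tests only (section 2), and maternal variables recorded but listed only as things to compare (section 3). Nothing in the plan would remove the effect of an imbalance.

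**Step 2: assumed bias.** All inputs are assumptions.
- Parity: 60% nulliparous in cases v 35% in controls, marker 0.4 SD higher in nulliparous women. Bias = (0.60 − 0.35) × 0.4 = 0.10 SD.
- BMI: 3 kg/m² higher in cases, 0.05 SD per kg/m². Bias = 3 × 0.05 = 0.15 SD.
- Same direction: 0.10 + 0.15 = 0.25 SD. Opposite directions: 0.10 − 0.15 = −0.05 SD.

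**Step 3: false-positive rate for 31 v 31, two-sided 5% (assumed), no true disease effect.**
SE = √(1/31 + 1/31) = 0.254 SD. With k = bias/SE, rate = Φ(−1.96 + k) + Φ(−1.96 − k).

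| Net bias (SD) | k | Rate |
|---|---|---|
| −0.05 | −0.197 | 5.4% |
| 0.10 | 0.394 | 6.8% |
| 0.15 | 0.591 | 9.1% |
| 0.25 | 0.984 | 16.6% |

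For 30 v 33, SE = √(1/30 + 1/33) = 0.252 SD, and biases of 0.10 and 0.25 SD give 6.8% and 16.8%. Exact noncentral-t values are lower by less than half a percentage point.

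**Step 4: simulation as a cross-check.** One covariate shifted by d SD between cases and controls, with correlation ρ to the marker within groups; 3,000 runs per setting; 31 v 31; no disease effect.

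| d | ρ | Bias d × ρ (SD) | Unadjusted | Covariate in model |
|---|---|---|---|---|
| 0.3 | 0.2 | 0.06 | 5.6% | 4.9% |
| 0.5 | 0.2 | 0.10 | 7.6% | 5.5% |
| 0.5 | 0.5 | 0.25 | 16.6% | 4.6% |

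Modelling the covariate restores the rate to about 5%. This assumes that it is measured without error and that the linear form is right.

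**Step 5: would a baseline test show the imbalance?** For 31 v 31 at two-sided 5%:
- Nulliparity 60% v 35%: the pooled proportion is 0.475, so the null SE is √(2 × 0.475 × 0.525/31) = 0.1268. The SE under the alternative is √((0.60 × 0.40 + 0.35 × 0.65)/31) = 0.1228. Power = Φ((0.25 − 1.96 × 0.1268)/0.1228) ≈ 50%.
- BMI gap of 3 kg/m²: power about 64% if the SD is 5 and about 49% if it is 6 (noncentral t).

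So an imbalance of the assumed size would go undetected in roughly a third to a half of studies like this one.

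**Step 6: scale.** At 80% power and two-sided 5%, the detectable difference for 31 v 31 is (1.960 + 0.842) × 0.254 = 0.71 SD. A bias of 0.25 SD could create or inflate a modest finding, but would not by itself explain a very large one.

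**The case against.** **Silence is not evidence of unrestricted selection.** A reader might infer that controls were chosen without regard to parity, age or BMI. The documents do not say that. Eligibility is deferred to sources we cannot see, and a restriction there cannot be excluded. This stands: the supportable statement is that none is stated.

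**Confounding needs two links, and neither is in the documents.** Nothing there says that cases differ from controls on these factors, or that either marker varies with them. This also stands. A reader might infer that both endpoints are biased; the documents support only that the case-control comparison is unprotected. If the effects of body size and parity work in opposite directions, the false-positive rate could stay near 5%.

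**Pooled figures would look worse.** Treating the study as 61 v 64 gives larger rates for the same bias, but that does not describe a comparison within the early or late pair, so those rates are not used here.

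**An unadjusted difference is a legitimate descriptive quantity.** For a marker study this is fair, and it is why the unadjusted result should stay. It does not help a reader judge how much of the difference belongs to the disease.

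**The plan already compares the groups on these variables and discloses the missing pre-pregnancy BMI.** Gross imbalance would be visible. That does not adjust for it, and Step 5 shows how weak the check is.

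**The primary adjusted model leaves BMI out.** On the assumed figures it removes 0.10 SD of the 0.25 SD and leaves 0.15 SD, a false-positive rate of about 9%. This is a real limit, and the reason for the second model with BMI.

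**Conclusion.** The point holds in a limited form. The plan states no matching or restriction of controls on parity, maternal age or BMI beyond the 34-week stratum, and makes no use of these recorded variables in comparing MMP-14 and s-ENG between cases and controls. The only tests it names do not adjust, and they appear under Baseline Characteristics; applying them to the markers is the natural reading because no other method is given.

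The case-control part of both endpoints is therefore open to confounding. How large it is, and in which direction, cannot be learned from the documents. The range of about 7% to 17% for 31 v 31 rests on an assumed net bias of 0.1 to 0.25 SD, a 5% two-sided level and no true effect; it shows scale and is not an estimate for this study. No figure is offered for maternal age.

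**What to change.** Add to the analysis plan, for each marker separately in the early pair (groups 3 v 4) and the late pair (groups 1 v 2):

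1. Estimate the case-control difference, with a 95% confidence interval, from a linear model containing group, parity (nulliparous or parous) and maternal age. Report it beside the unadjusted result.
2. Repeat with recorded BMI added, labelled as a sensitivity analysis, because BMI measured after onset may include oedema and so partly reflect the disease.
3. State in one sentence how controls were chosen, and whether the eligibility criteria restrict age, parity or BMI.

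The cost is two models per marker in each pair on data already recorded, using two degrees of freedom for the covariates, or three with BMI, in pairs of 62 or 63 women. Control selection should not be changed now: the document is dated June 2018 within a January to December 2018 recruitment period, and matching only the remaining controls would mix two selection schemes.

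### Nothing planned protects the group 3 versus group 4 comparison of MMP-14 and s-ENG from a difference in gestational age at sampling

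*Combined protocol and SAP*

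**What the plan says.** **Groups (1. Participant Flow, Recruitment Details).** Of the two groups below 34 weeks, the case group is defined as "31 early-onset preeclampsia patients as group 3 (gestational age < 34 weeks". Its control counterpart is given in the same terms: "31 patients with normal pregnancies as group 4 (gestational age < 34 weeks". Both have an upper limit; neither has a lower one. On recruitment: "The authors consecutively recruited 61 pregnancies complicated with preeclampsia, and 64 healthy pregnancies will select for the control group". Nothing is said about matching by week.

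**Eligibility (1. Participant Flow, Pre-assignment Details).** The criteria are not listed: "The inclusion criteria were maken according to the official documents". A lower week limit may therefore exist elsewhere.

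**Sampling (3. Outcome Measures).** Cases gave blood for both marker "levels after the diagnosis of early/late onset preeclampsia in outpatient clinic". For controls: "The control group's samples were obtained during routine obstetrical care examination in the third trimester of pregnancy". The week at which the third trimester begins is not given.

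**Analysis (2. Baseline Characteristics).** The only tests named anywhere are in this sentence: "t-test was used for comparison of two groups and one-way analysis of variance was used for comparison of three groups". Section 3 lists the variables compared across the four groups, including both markers and gestational week, but does not spell out the marker contrast. It also says: "The demographic data for gestational age, gravidity, parity, maternal age and BMI was recorded". It does not say that this is gestational age at blood sampling.

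**Endpoints and limitations.** MMP-14 is the primary and s-ENG the secondary marker (4. Endpoints of the study). Section 5 does not mention gestational age at sampling.

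**The concern.** Cases and controls below 34 weeks enter under different timing rules. A control is sampled at a routine visit in the third trimester; a case is sampled whenever the disease is diagnosed. The split at 34 weeks controls gestational age between the two strata but not within the lower one.

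Group 3 versus group 4 is the case-control contrast that the grouping implies below 34 weeks. Confounding of it needs two things: a gap in mean week at sampling, and a marker level that changes with gestation. If both are present, an unadjusted test attributes the gestational-age part of the difference to preeclampsia. Any case sampled before the third trimester would also have no control at a comparable week.

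Groups 1 and 2 carry a smaller risk, since every woman from 34 weeks on is in the third trimester. No magnitude is claimed for them.

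**Working it through.** **Inputs from the documents.** Group sizes are 31 and 31. The counts agree: 30 + 31 = 61 cases, 33 + 31 = 64 controls, 125 in all. The plan gives no significance level, standard deviation, effect size, marker trend or distribution of weeks, so there is no figure of its own to reproduce. What follows is an illustration.

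**Assumed inputs.** Two-sided 5% test, no true disease effect, residual SD of 1 at a fixed week, and a linear trend of *b* SD per week common to cases and controls.

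**Step 1, closed form.** If mean week differs by *D*, the spurious difference is d = D × b. The t-test on 60 df has noncentrality d / √(2/31) = d / 0.254. For D = 1 and b = 0.10, d = 0.10 and the noncentrality is 0.39, so the test rejects in 6.7%.

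| Gap in mean week | b = 0.05 | b = 0.10 | b = 0.20 |
|---|---|---|---|
| 1 | 5.4% | 6.7% | 12.1% |
| 2 | 6.7% | 12.1% | 34.1% |
| 4 | 12.1% | 34.1% | 87.3% |

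A 4-week gap corresponds to controls spread evenly over 28–34 weeks (mean 31) and cases over 20–34 (mean 27). With D = 0 or b = 0 the rate stays at 5%.

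**Step 2, simulation.** There are 20,000 runs per scenario (Monte Carlo error about ±0.3 points at 5%). Control weeks are uniform on 28–34. Of the 31 cases, *k* are uniform on 20–28 (mean 24) and the rest uniform on 28–34 (mean 31). The expected gap is (k/31) × (31 − 24) = (k/31) × 7 weeks. The adjusted test is a linear model with status and gestational age (59 df).

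| Early cases, k | Gap (weeks) | Unadjusted, b = 0.10 | Unadjusted, b = 0.20 |
|---|---|---|---|
| 3 | 0.68 | 5.4% | 6.6% |
| 6 | 1.35 | 7.4% | 13.8% |
| 9 | 2.03 | 11.3% | 26.0% |

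The adjusted test rejects in 4.5% to 5.4% throughout. The simulated rates lie below the closed form at similar gaps because the spread of weeks adds to the within-group SD, which the closed form holds at 1.

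**Step 3, varying the assumptions (unadjusted rates).**

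- *k* = 0, both groups uniform on 28–34: 4.8% to 5.5%, no inflation.
- No early case, but cases uniform on 30–34: the gap is 32 − 31 = 1 week in the other direction, and the rates are 6.6% and 11.2% for b = 0.10 and 0.20. Inflation therefore does not need cases before 28 weeks.
- Early cases from 24 instead of 20 weeks: the gap is (k/31) × 5 = 0.48, 0.97 or 1.45 weeks for k = 3, 6, 9. The rates are 5.1%, 6.3%, 8.2% for b = 0.10 and 6.0%, 9.2%, 16.4% for b = 0.20.
- b = 0.05 with the 20–28 window: 5.4%, 5.5%, 6.6% for k = 3, 6, 9.
- Trend only from 28 weeks on: 5.1% to 9.3%. The adjusted test rejects in 4.7% to 5.4%, with its estimate off by 0.02 to 0.05 SD.

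**The case against.** The strongest reply is that neither ingredient of the bias is in the documents: no gap in week is shown, no marker trend is given, and a lower limit for cases may sit in the eligibility documents that are not reproduced. That is correct, and it is why this is called a risk.

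The design already pairs each case group with controls on the same side of 34 weeks, and it compares gestational week across groups. The first point removes the coarse imbalance and leaves what lies within the stratum. The second can reveal a gap but does not take it out of the marker comparison, and with 31 per group a non-significant difference in week would not exclude a relevant one.

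The size depends heavily on assumed inputs. A floor of 20 weeks may be too low: the recording of infant weight at delivery in all groups suggests, without proving, pregnancies carried towards live birth. With a floor of 24 weeks the largest rate falls from 26% to 16%, and with a shallow trend the rates stay close to nominal. This stands: the percentages illustrate a mechanism and are not evidence about this study. It cuts both ways, since the absence of inflation with no early cases holds only when weeks are spread alike in both groups.

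Finally, gestational age at sampling in cases is close to week at diagnosis, so adjustment may absorb some disease timing or severity, which the endpoints also address. That is a real cost, and a reason to report adjusted results alongside the distribution of weeks.

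**Conclusion.** The point holds as a design risk. The text supports each element: third-trimester sampling for controls, sampling at diagnosis with no stated lower week for cases, no described matching by week, and unadjusted tests only. Whether the bias is present, and in which direction, cannot be told from the documents; it may be zero.

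Under the assumed inputs, the unadjusted false-positive rate runs from nominal to about 14% with up to 6 early cases of 31. It reaches 26% only when the steepest trend (0.20 SD per week) and the largest count (9 of 31) are combined. Adjustment brings it back to about 5%. The change is cheap and bears on both marker endpoints, so it should be made; confidence is medium because the inputs that set its importance are unknown.

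**What to change.** **Change.** Analyse MMP-14 and s-ENG within each stratum, or in one model with status, stratum and their interaction, with continuous gestational age at blood sampling as a covariate. Report the adjusted group 3 versus 4 and group 1 versus 2 differences with 95% confidence intervals. State that the model assumes a linear slope common to cases and controls, and plot each marker against week by group to check it. Add a sensitivity analysis restricted to weeks covered by both cases and controls, because adjustment for a case sampled before the third trimester extrapolates beyond every control.

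For this to work, confirm that the recorded gestational age is that at sampling, state the week that starts the third trimester and the lower limit for group 3, and report gestational age by group (mean, SD, range).

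**Cost.** SAP wording and one covariate. In the simulated 31 versus 31 stratum with no trend:

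| Early cases | Mean SE, unadjusted → adjusted | Increase | Power for 0.8 SD: unadjusted / adjusted / restricted and adjusted |
|---|---|---|---|
| 3 | 0.2531 → 0.2571 | 1.6% | 87% / 86% / 85% |
| 6 | 0.2529 → 0.2620 | 3.6% | 87% / 85% / 82% |
| 9 | 0.2527 → 0.2689 | 6.4% | 87% / 83% / 79% |

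If the common slope fails (controls flat, cases rising by 0.10 or 0.20 SD per week, no difference at 31 weeks), the adjusted estimate is off by 0.02 to 0.08 SD and its test rejects in 5.0% to 5.8%. The restricted analysis rejects in 4.9% to 5.1%.
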